1.3.2 Known Potential Benefits

Benefits of this research are collection and presentation of detailed 6-month outcomes on an already implemented CRAG screen-and-treat programme across South Africa. This will highlight gaps in the care cascade, and areas for improvement of the programme in the future.

2 OBJECTIVES

2.1 Study Objectives

We seek to evaluate how best to optimize implementation of reflex laboratory CrAg screening in real-world facilities across South Africa in order to improve the HIV care continuum and thus maximize the survival of persons living with AIDS.

Primary objective (Years 1 and 2): To implement enhanced surveillance at selected sites to determine the outcomes (overall and for pre-specified subgroups) of a national reflex laboratory CRAG screening and pre-emptive treatment programme in South Africa.

Primary objective (Years 2-5): To implement and test programmatic interventions to improve 6-month cryptococcal-free survival.

Examples may include:

- a) Enhanced diagnostics to customize or differentiate patient care
 - a. Using CRAG titre results (e.g. ≥160 titre) to guide when to recommend to perform lumbar puncture (LPs) to detect subclinical meningitis
 - b. Using CRAG titre results to guide recommendations for enhanced antifungal therapy
 - c. Validate CRAG diagnostics
- b) Healthcare provider training
 - a. Training in an online/digital creative format
 - b. Refresher training: Determine frequency of refresher training associated with adherence to national protocols and patient outcome
 - c. Patient education
- c) Enhanced laboratory services: Determine benefit of enhanced methods to deliver CD4 and CRAG results to requestors
 - a. Using SMS to healthcare providers (or SMS alerts to patients to return to the facility for urgent results)
 - b. Contacting patients directly with CRAG results with provision of simple instructions for required next steps
 - c. Confidential "results for action reports" to district and facility managers (i.e. line lists of CRAG+ patients and patients with a CD4<100 but no CRAG test result)

Secondary Objectives:

2. Evaluate cost-effectiveness of a real-world CRAG screening and pre-emptive treatment programme on the ground in South Africa.

3. Evaluate risk factors for treatment failure.

Exploratory Objectives:

- 4. Measure the impact of same day test and treatment on timing of ART initiation among CRAG+ and CRAG negative individuals.
- 5. Describe the prevalence of opportunistic infections in CRAG+ and CRAG negative individuals

2.2 Study Outcome Measures (Overall and For Pre-Specified Subgroups)

2.2.1 Primary Outcome Measures (years 1-5)

1. 6-month cryptococcal meningitis free-survival

2.2.2 Secondary Outcome Measures

- 1. 6-month retention in care
- 2. Operational challenges of implementation including:
 - a. Time from CD4 testing, CRAG testing, antifungal therapy, and ART initiation among those with a CRAG+ result
 - b. Proportion of CD4/ CRAG results that are received, acknowledged and acted upon by a health practitioner
 - c. Proportion of patients with advanced disease receiving TB screening
 - d. Proportion of CRAG+ persons who develop symptomatic cryptococcal meningitis
 - e. Completion of lumbar puncture when clinically indicated
 - f. Availability of lumbar puncture and appropriate antifungal therapy in routine clinical practice
 - g. Loss to follow-up after CRAG screening and/or during antifungal therapy
 - Proportion of clinicians and staff trained on the CRAG screening algorithm and CRAG lateral flow assay (LFA) (the latter only for facilities that are distant from a laboratory)
 - i. Adherence to CRAG screening and pre-emptive treatment guidelines by healthcare practitioners
- 3. Costs of CRAG+ treatment programs, Incremental cost-effectiveness ratio (ICER)

2.2.3 Exploratory outcome measures:

- 1. Time to ART initiation in test and treat programs amongst HIV-infected persons with advanced disease.
- 2. Prevalence of opportunistic infections in HIV-infected persons with advanced disease

3 STUDY DESIGN

This is an evaluation of an ongoing national screening programme. In years 1 and 2, we will implement an enhanced metrics and evaluation project at selected sites in all provinces across South Africa to measure 6-month outcomes of this programme, along with operational challenges. In years 2 to 5 we will implement programmatic strategies to maximize 6-month cryptococcal meningitis-free survival.

Per South African standard of care, those with a CD4<100 cells/µL will reflexively get a CRAG test performed on remaining blood specimen. We expect the majority of these persons to be asymptomatic outpatients presenting for routine HIV care, though a small proportion will be persons who present to care because they feel unwell. All participants will receive standard of care treatment for asymptomatic cryptococcal antigenaemia, per South African HIV guidelines.

Primary Objective (years 1 and 2): To implement enhanced surveillance at selected sites to determine the outcomes (overall and for pre-specified subgroups) of a national reflex laboratory CRAG screening and pre-emptive treatment programme in South Africa. We estimate performing enhanced surveillance at **approximately 400 clinics out of 4500 clinics nationally**. A list of surveillance facilities will be agreed upon in discussion with provincial departments of health.

We will assess the cascade of care from CD4 testing to CRAG testing, to receipt of CRAG results by healthcare provider, assessment for symptoms, lumbar puncture if indicated, preemptive treatment for those asymptomatic, and 6-month outcomes.

The initial surveillance performed in Objective 1 will establish **baseline 6-month CRAG+ outcomes** (Year 1 and 2) from which subsequent programmatic interventions will seek to improve.

Subgroup Analyses

A number of subgroup analyses will be performed to understand optimal CRAG screening and treatment programmes. For example, we will compare outcomes amongst CRAG+ persons who:

- a) initiated on ART before CD4/ CRAG results are known (same-day ART initiation in the context of universal HIV test-and-treat) to those who have ART delayed until a minimum of 2 weeks of antifungal treatment completion
- b) rural clinics vs. urban centres
- c) high titres (\geq 160) vs. low titres (<160)

- d) clinics that routinely perform lumbar punctures to those that are unable to perform lumbar punctures (stratified by titre)
- e) development of culture-positive cryptococcal meningitis. These lab results will be captured by the NHLS database, and additional queries by NICD personnel of medical records of CSF CRAG+ persons will be performed for secondary data review and quality assurance on the rate of capture of meningitis episodes. The GERMS surveillance system run by NICD will continue to capture cryptococcal meningitis among those lost to follow up or who transfer care.
- f) Cryptococcal meningitis-free survival of those who receive secondary prophylaxis vs. none
- g) Special populations: pregnant women, those with liver disease.

Such information will be particularly nuanced to the South African CRAG screening and treatment programme, but will also be informative to other sites in sub Saharan Africa that are initiating similar national programmes.

Active enhanced surveillance

Data will be collected by two methods:

A) primary (retrospective) data collection by chart/ record review at facility level by partners and B) secondary analysis and triangulation of existing laboratory and surveillance datasets.

Primary data collection by partners

We will collaborate with partners in South Africa to conduct active surveillance of all CRAG+ persons at selected facilities using a standardized data collection tool (attached – version 1.0, 4 January 2017). Please see appendix for list of partners, and potential roles. Partners may assist with monitoring and evaluation, capturing health information, contact tracing of those who are lost-to-follow up, and/or collecting operational information.

Partners will review patient demographics and outcomes of those who are CRAG+ by retrospective chart/ record review. This will be performed approximately 3 times over a 6-month period, to obtain information about CRAG result, CD4 result, presence of CNS symptoms, receipt of fluconazole if appropriate, and triage to lumbar puncture if symptomatic, along with timing of ART initiation, 6-month survival, retention-in-care, and incidence of cryptococcal meningitis.

Surveillance will not occur at all facilities across South Africa, but at selected facilities within each South African province. A list of surveillance facilities will be agreed upon in discussion with provincial departments of health.

Secondary analysis and triangulation of existing datasets noted on pages 13 and 14.

- Cohort of those with advanced HIV (CD4 <100), incl. CRAG results
 - Subset of those with a positive CRAG result
 - o Subset of those with cryptococcal meningitis

Primary objective (Years 2-5): To implement and test programmatic interventions to improve 6-month cryptococcal-free survival.

Starting in Year 2, we will use the data generated from the preceding years regarding the barriers in the cascade-of-care to identify areas which may require programmatic interventions to improve 6-month CRAG+ outcomes. Such interventions will be implemented at selected enhanced surveillance facilities to determine their effectiveness (pre/post intervention) as well as compared with facilities without the intervention. The exact intervention(s) to be implemented will be dependent on the challenges observed during the initial surveillance. Examples may include:

Intervention 1: Stratification by CRAG titre

For a subset of CRAG+ persons in the enhanced surveillance cohort, we will perform CRAG titres. We anticipate performing these retrospectively (batched) initially, and then for a short time prospectively to evaluate whether this is feasible in the lab. CRAG titres will not be reported to treating clinicians initially. Once data have been collected in years 1 and 2 regarding outcomes of those with high CRAG titres vs. low CRAG titres, we may then routinely report CRAG titre results with CD4 results. An information sheet may be attached to the lab results educating healthcare workers of the CRAG+ result and suggestions for management. Alternatively, this

information will be included in routine healthcare worker training materials. We may recommend that those with a CRAG titre \geq 160 have a LP performed to evaluate for meningitis, given that these persons are at high risk for meningitis and death. The outcome will be 6-month survival.

We hypothesize those with CRAG titres \geq 160 will benefit from recommended lumbar punctures to detect occult meningitis (defined as CSF CRAG+ and/or culture-positive) in comparison with those who decline LPs. Conversely, we hypothesize those with low CRAG titres <160, do not have a survival benefit when receiving LPs (i.e. due to low prevalence of asymptomatic occult meningitis).

Intervention 2: Healthcare provider training

- We will create online/digital training programs for laboratory workers, health care providers, and clinic staff regarding CRAG screening and pre-emptive treatment. Alternatively, we will partner with existing initiatives such as Project ECHO (continuing professional education and clinical mentoring via zoom video conferencing). These educational programs will be implemented at clinics to evaluate whether gaps in the cascade of care can be minimized.
- We will create refresher training for lab workers, health care providers, and clinic staff regarding CRAG screening and pre-emptive treatment, and measure if more frequent training sessions improve adherence to national protocols and patient outcome.
- Finally we will create patient education materials in the form of posters that can be hung in clinic waiting rooms, short presentations that can be performed by community healthcare workers in clinic waiting rooms/ as part of focus groups, and digital training programs for patients. We will measure overall clinic adherence to national protocols and patient outcomes. Sample educational materials below.

Intervention 3: Determine benefit of enhanced methods to deliver CD4 and CRAG results

- a) SMS may be used for clinic appointment reminders, medication adherence reminders, and general information, as a potential method to enhance retention in care of CRAG+ persons. SMS may be used by clinics to enhance the cascade of care, for example, to report anticipated fluconazole stockouts, or to remind providers to perform TB screening for those with advanced HIV disease.
- b) Reports for each district and facility managers with line list of CRAG+ patients, and those with a CD4<100 without CRAG testing (compare outcomes in districts/ facilities with Result for Action reports vs. no Result for Action reports)
- Intervention 4: Enhanced antifungal therapy based on CRAG titre. After years 1 and 2, outcomes of those with high/low CRAG titres will have been summarized. We hypothesise that those with high CRAG titres would have higher mortality and would be at higher risk for breakthrough meningitis, as seen in multiple other studies.

If this is the case, we may then select a small number of high volume sites to perform CRAG titres in real time, and recommend enhanced antifungal therapy for those with high CRAG titres. Please note: This will be a separate ethics committee submission and will include informed consent from participants.

Secondary Objectives:

1. Evaluate cost-effectiveness of real-world CRAG screening and pre-emptive treatment programmes in South Africa.

Cost-effectiveness of CRAG screening and pre-emptive treatment has been evaluated in South Africa using mathematical modelling. However, real-world costs and implementation have not been accounted for. For example, this prior model did not account for the repeated training sessions required for healthcare workers. Theoretical models typically don't account for challenges that are seen on the ground, such as fluconazole stock outs, point-of-care CD4 testing, and variable performance and acceptance of lumbar punctures. Effectiveness will be obtained from Objective 1. Analysis will be from the perspective of the health care payer. We will map out the flow of CRAG screen and treat through the HIV cascade of care.

Costs will be collected on health care workers' salaries and percent effort dedicated to CRAG screening, training, lab testing, transport of lab results, fluconazole, and further evaluation of symptomatic patients such as lumbar puncture will be incorporated. Cost of hospitalization and treatment of cryptococcal meningitis will be an important consideration, and will likely vary depending on hospital site. Cost-outcome measures will include annual cost per patient, cost per death prevented, cost of meningitis-free survival, and cost per quality-adjusted life year gained. Cost effectiveness ratios will be stratified by CRAG titre threshold. Incremental cost-effectiveness ratio (ICER) with interventions from Aim 2 will be compared to Aim 1.

Costs and effectiveness will be stratified by subgroups. For example, we expect variable cost and efficacy amongst:

- a) Rural vs. urban clinics
- b) Clinics where LPs are feasible vs. those that are not
- c) Patients that receive secondary prophylaxis vs. those who stop fluconazole without prophylaxis
- d) High CRAG titre vs. low CRAG titre
- e) Education and Retention-in-care: Efforts for education of patients and healthcare workers, and efforts to improve retention in care such as using SMS will likely be more costly at the clinic level. However, if proven to be efficacious (compared to without these interventions) may be cost-effective interventions.

Probabilistic sensitivity analysis will be performed thereafter to account for uncertainty in parameter such as loss to follow up, or performance of lumbar punctures –which will likely vary by site. This will yield more nuanced data regarding the efficiency of CRAG screening programs, and important barriers to overcome for comprehensive, cost-effective care.

2. Evaluate risk factors for treatment failure.

The purpose of this objective is to define high-risk populations that may require customized, intensive care in the future. We hypothesize that high initial CRAG titres in blood (≥160), is a risk factors for meningitis and death. Preliminary data from the original ORCAS study in Uganda from 2012 to 2014 suggests that CRAG titre is a risk factor for death.

Other risk factors may include rapid or same-day ART initiation, delay in ART initiation >2 weeks from initial CD4 blood draw, delays in initiation of fluconazole beyond 2 weeks from initial CD4 blood draw, stock outs of fluconazole, etc.

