8.1 Statistical Analysis Plan

The rate (with 95% confidence interval) for the primary and secondary events will be estimated overall and for pre-specified subgroups during the first 2 years of the study. Those rates will subsequently be compared with the rates after programmatic changes have been made (during years 2-5) to increase the effectiveness of the national screening program.

For the subgroups we will also use time-to-event methods to compare the primary and selected secondary endpoints. The table below reports detectable hazard ratios for the primary event with 80% and 90% power, assuming a two-sided alpha=0.05, 70% CM-free survival in the control group, and the stated number of subgroup participants. For example, if CSF CRAG titre data are available for 1200 participants (with 300 having a titre \geq 160), then we can detect a hazard ratio as small as 1.37, for an almost 10% difference in event-free survival.

Detectable Hazard Ratios for Subgroups					
(Assuming two-sided α =0.05 and 70% event-free survival in the control group)					
		80% Power		90% Power	
	N per		Proportion		Proportion
Subgroup	group	HR	Surviving	HR	Surviving
High CSF CRAG titre	300	1.37	0.61	1.44	0.60
(≥1:160)					
Control	900				
(CSF CRAG titre < 1:160)					

The a priori subgroups of interest are:

- High CRAG titres (\geq 1:160) vs. low titres (<1:160)
- Male vs. Female
- Pregnant vs. Non-pregnant
- Liver Disease (ALT>3x Upper Limit of Normal) vs. No liver disease

- Geographic Location (urban vs. rural)
- Timing of ART Initiation
 - On pre-existing ART
 - Initiated on ART before CD4/ CRAG results are known (same-day ART initiation in the context of universal HIV test-and-treat)
 - ART initiated at 2 weeks
 - ART initiated at >=4 weeks
- Clinic-level outcomes (i.e. cluster) based on proportion of CRAG+ persons receiving Lumbar Punctures.
- Duration of fluconazole use
- Fluconazole secondary prophylaxis vs. none

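### Section 8.1 reduces the Years 2-5 test of interventions to one pooled before/after comparison and drops the concurrent comparison that section 3 promises

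*Protocol*

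**What the plan says.** The primary objective for Years 2-5 is to implement and test programmatic interventions. Section 3 gives the test two parts. The first is before/after: "Such interventions will be implemented at selected enhanced surveillance facilities to determine their effectiveness (pre/post intervention"). The same sentence adds the second, a concurrent one: "as well as compared with facilities without the intervention". Intervention 3 repeats the concurrent idea for one component: "compare outcomes in districts/ facilities with Result for Action reports vs. no Result for Action reports".

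Section 8.1 has one sentence for this objective. After describing the Years 1-2 rates it says: "Those rates will subsequently be compared with the rates after programmatic changes have been made (during years 2-5"). It names no comparator facilities and does not distinguish one change from another.

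The cost-effectiveness text in section 3 is grouped in the same way: "Incremental cost-effectiveness ratio (ICER) with interventions from Aim 2 will be compared to Aim 1". Item e) of its list of strata does mention a comparison with settings lacking the education and retention efforts.

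The interventions are not fixed. Four are listed as examples, and "The exact intervention(s) to be implemented will be dependent on the challenges observed during the initial surveillance".

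**The concern.** Sections 3 and 8.1 describe different analyses of the same objective. Anyone working from 8.1 would compare Years 1-2 rates with later rates and stop there.

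That comparison cannot say which change produced a difference, or whether any did, since outcomes may drift over calendar time. The protocol also has no rule on allocating, staggering or recording interventions by facility. A facility could therefore have two interventions, and a facility counted as lacking one could be receiving another.

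At stake is attribution. A component that does nothing, run beside one that works, could be credited with the benefit. It could then carry that benefit into an incremental cost-effectiveness ratio (ICER) and be recommended for wider use.

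**Working it through.** **The plan's own figure.** The only power figure in the protocol is the titre subgroup table in section 8.1 (300 against 900 participants, 70% event-free survival in controls, two-sided 0.05). Survival in the high-titre group is 0.70^1.37 = 0.61 and 0.70^1.44 = 0.60, as tabulated. A two-proportion calculation gives power of 78.7% and 89.6% against the stated 80% and 90%. The table reproduces, but it concerns titre, not a Years 2-5 intervention, and does not bear on this point.

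**Step 1. What each comparison estimates.** Take two interventions A and B with additive effects a and b, and a calendar change t between periods.
- Before/after with both interventions running: t + a + b.
- Before/after with only A running: t + a. Calendar time remains mixed in even here.
- Change in facilities with A minus change in facilities without A, where a share p of the first group and a share q of the second also have B: (t + a + pb) − (t + qb) = a + (p − q)b.

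The concurrent comparison removes t. It is free of B when p = q, and is off by (p − q)b otherwise unless the analysis uses each facility's exposure to B.

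**Step 2. What can be identified.** Fit intercept, period, A and B (4 parameters) to facility-by-period data. Every facility has a baseline row (1,0,0,0). The later-period rows depend on the layout:

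| Layout | Later-period rows | Rank of 4 | What can be estimated |
|---|---|---|---|
| 1. Before/after only, A and B in every facility | (1,1,1,1) | 2 | t + a + b only |
| 2. Untreated facilities included, A and B always together | (1,1,0,0), (1,1,1,1) | 3 | the bundle a + b |
| 3. Untreated facilities included, A and B in different facilities | (1,1,0,0), (1,1,1,0), (1,1,0,1) | 4 | a and b separately |
| 4. Partial overlap: neither, A only, B only, both; no interaction | (1,1,0,0), (1,1,1,0), (1,1,0,1), (1,1,1,1) | 4 | a and b separately |

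Layout 1 is the section 8.1 comparison with more than one intervention running. Layouts 2 to 4 are what section 3 makes possible. Layouts 3 and 4 need facilities with neither intervention. If A's only comparators all have B (p = 0, q = 1), Step 1 gives a − b.

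**Step 3. Does the text allow overlap?** It does not exclude it, and in places it points that way. Under Intervention 1, the titre advice may alternatively be delivered through training: "information will be included in routine healthcare worker training materials". Intervention 4 would use real-time titres, so it would coincide with titre testing at its sites. Result for Action reports go to districts as well as facilities, so one could reach clinics that have another intervention. None of these sentences says that overlap will occur.

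**The case against.** The strongest objection is that overlap is an inference. No sentence puts several interventions in the same facilities at the same time. The four are examples, and perhaps only one will be used. The training-materials route is optional and need not be Intervention 2's new programme. Intervention 4 is confined, in that "we may then select a small number of high volume sites to perform CRAG titres in real time", and needs a separate ethics submission. Section 9.2 requires an amendment for anything beyond standard of care. All of this stands.

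A reader might therefore infer too much: that the interventions do overlap and that no single effect or ICER can be recovered. The documents do not support that. Section 3 promises facilities without the intervention, and Step 2 shows that separation then fails only in particular layouts, chiefly full coincidence.

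It can also be said that no ICER per intervention is promised, so Aim 2 against Aim 1 may be a deliberate programme-level ratio. That is a fair reading, and the grouped ratio is not in itself an error. The point applies only if a ratio is attributed to a single intervention.

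Finally, model terms usually belong in a statistical analysis plan, which is not shown. That would excuse silence in section 8.1. It does not excuse 8.1 stating a comparison that omits half of the one in section 3.

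**Conclusion.** The point holds as a mismatch between sections 3 and 8.1, with a conditional consequence. Section 8.1 drops the concurrent comparison and pools the changes. If more than one intervention runs, that comparison cannot separate one effect from another or from calendar time (rank 2 of 4). The comparison in section 3 can do so (rank 4 of 4) if the interventions do not fully coincide, some facilities have neither, and the analysis uses each facility's exposure. If they do fully coincide, only the bundle is estimable (rank 3 of 4).

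The conclusion assumes additive effects without interaction. It also assumes that facilities with and without an intervention would otherwise have changed alike, which matters because facilities are selected rather than randomised. The protocol gives no intervention effect and no overlap fraction, so the bias can be written as (p − q)b but not put in percentage points. The documents do not show that overlap will happen, only that nothing prevents it.

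**What to change.** Align section 8.1 with section 3. Replace the pooled before/after sentence with a facility-level analysis that:
- includes facilities without the intervention;
- has one time-varying term per intervention, set from the recorded start date in each facility;
- has a term for calendar period;
- allows for clustering by facility.

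In the cost-effectiveness section, say that any intervention-specific ICER takes its effect from that intervention's own term. Where interventions start together in the same facilities, report the effect and the ICER for the bundle only. A programme-level ratio of Aim 2 against Aim 1 can stay if it is labelled as such.

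The cost is revised wording, a record of which facility started what and when, and some analysis work. No further patient data are needed. Start dates should be recorded from the first intervention onward. Avoiding simultaneous starts where feasible would help but is optional. Compulsory spacing or factorial allocation would constrain a public programme that may have good reason to deliver a bundle, and this point does not require it.

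### Every numeric titre comparison in the protocol is one split at 160, which tests that cut but cannot show whether risk is graded or steps at another titre

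*Protocol*

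**What the plan says.** All references are to the protocol.

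- **Where a number is given, it is 160.** Section 3 uses it in Subgroup Analyses item c, in both Intervention 1 hypotheses and in the risk-factor hypothesis (second secondary objective). Section 8.1 uses it in the list of a priori subgroups (high titres "vs. low titres (<1:160") and in the power table.
- **Elsewhere the wording is looser.** Intervention 4 speaks of high and low titres without a figure. The cost-effectiveness text says "Cost effectiveness ratios will be stratified by CRAG titre threshold" and names no value. Section 2.1 gives the value as an example: "Using CRAG titre results (e.g. ≥160 titre) to guide when to recommend to perform lumbar puncture".
- **Origin of the cut.** Section 1.1, in the knowledge gap on treatment regimen, cites preliminary results from a Ugandan trial for titres of 160 or more together with a CD4 count below 50.
- **Use of the Years 1-2 data.** Routine titre reporting and a possible lumbar puncture recommendation may follow "Once data have been collected in years 1 and 2 regarding outcomes of those with high CRAG titres vs. low CRAG titres". Intervention 4 may follow if high titres prove to carry higher risk.
- **Data collected.** The patient-level table in section 5 lists the titre as an item. It does not say whether the end-point dilution is recorded.
- **Power.** Section 8.1 works an illustration, "if CSF CRAG titre data are available for 1200 participants (with 300 having a titre" at or above 160): "then we can detect a hazard ratio as small as 1.37, for an almost 10% difference in event-free survival".

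**The concern.** A two-group contrast answers one question: do patients at or above 160 do worse than those below? A positive answer is expected whether risk climbs with each dilution, steps up below 160, or steps up well above it. The stated analysis would therefore show that titre matters without showing how risk is spread along the scale.

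That matters because the Years 1-2 titre results inform two possible interventions and the objective of defining high-risk populations. If risk already rises below 160, the Intervention 1 hypothesis about low-titre patients is examined in a group of mixed risk. If risk is concentrated far above 160, the high group is mixed instead.

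Timing adds to this. Titres are at first not reported to clinicians, so Years 1-2 are the cleanest period in which to describe the relation between titre and outcome. Once titre guides care, management will alter it.

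**Working it through.** **1. Inputs from section 8.1.** The calculation gives "detectable hazard ratios for the primary event with 80% and 90% power", "assuming a two-sided alpha=0.05, 70% CM-free survival in the control group", with 300 patients above the cut and 900 below (25% and 75%).

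**2. The protocol's own figure.** Use the log hazard ratio with variance 1/d1 + 1/d0, at HR 1.37:
- Survival in the high group: 0.70^1.37 = 0.613.
- Events: d1 = 300 × (1 − 0.613) ≈ 116; d0 = 900 × 0.30 = 270.
- Standard error: √(1/116 + 1/270) = 0.111.
- Power: Φ(ln 1.37 / 0.111 − 1.96) = Φ(0.876) = 0.81.

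Detectable HRs at 80% and 90% power by four methods:
- This variance: 1.37 and 1.43.
- Two-proportion formula: 1.38 and 1.44.
- Freedman: 1.36 and 1.42.
- Schoenfeld: 1.39 and 1.46.

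The stated 1.37 and 1.44 lie within these ranges. The table is sound for the binary comparison.

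**3. Information kept by the split if the effect is graded.** The protocol gives no titre distribution, so one must be assumed. For a normal log-titre with a log-linear effect, the fraction kept by a split with proportion p above the cut is φ(z)²/[p(1 − p)]. With p = 0.25 and z = 0.674:
- φ(0.674)² = 0.1010, and 0.25 × 0.75 = 0.1875.
- 0.1010 / 0.1875 = 0.539, and 0.539 × 1200 ≈ 646.

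On discrete doubling dilutions with 25% at or above 160, values off the low end placed at the lowest dilution, and an assumed SD of 1.5, 2, 2.5 or 3 doublings, the fraction is 0.56, 0.58, 0.62 or 0.65. The overall range is 0.54 to 0.65, a loss of 35% to 46%. At 0.654, 1200 patients act like about 785.

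**4. What this means for power.** Under the normal model, a split with 80% power has signal 1.960 + 0.842 = 2.802. The trend test has 2.802/√0.539 = 3.82, giving Φ(3.82 − 1.96) ≈ 0.97.

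**5. Dependence on shape.** Simulated score tests, 2000 runs each, N = 1200, SD 2 doublings, survival below 160 set at 0.70, no losses to follow-up:

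| True shape | Survival at ≥160 | Power, split at 160 | Power, linear log2 titre |
|---|---|---|---|
| Linear (log HR 0.085 per doubling) | 0.62 | 73% | 90% |
| Step at 40, HR 1.6 | 0.64 | 47% | 91% |
| Step at 640, HR 2 | 0.66 | 27% | 40% |
| Step at 160, HR 1.37 | 0.61 | 79% | 56% |

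All four shapes lower survival in the high group, to between 0.61 and 0.66. The split does not tell them apart. In the last row it is clearly the stronger test.

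**The case against.** **The form of a covariate is SAP detail.** A separate SAP, not available here, could add an ordinal or continuous analysis, and the section 3 subgroup list is introduced as examples. This stands in part: nothing in the protocol excludes more. But section 8.1 is itself headed as the analysis plan, and the two-level split is a stated choice there, in the a priori list and the power table. It is not mere silence.

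**The cut is pre-specified, not provisional.** A reader might infer from the single example wording in section 2.1 that 160 is a placeholder. The documents do not support that. Sections 3 and 8.1 fix it in advance on external data, and testing an external cut in a new population is proper. No objective asks Years 1-2 to find the best cut.

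**Nothing need be lost.** A reader might infer that the titre information is thrown away or that the study cannot examine other titres. The titre is a collected item in section 5, so if the dilution is recorded, a finer analysis remains possible. The limitation lies in the stated analysis, not necessarily in the data.

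**The size is fragile.** The 300-of-1200 split is conditional, and section 8.1 labels it a CSF titre, whereas the risk-factor objective concerns titres in blood. Those two places need reconciling. Only CRAG-positive patients are titred, so the distribution is truncated. These points stand, so the loss is given as a range.

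**Later steps are conditional.** The interventions are worded as possibilities, Intervention 4 needs a separate ethics submission, and changes beyond standard of care need an amendment. This lessens the consequence but does not supply the missing description of risk by titre.

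**Conclusion.** The point holds as a limitation of the stated analysis. The single split at 160 can show that high-titre patients do worse. It cannot show whether risk is graded or steps elsewhere, although the Years 1-2 titre results inform Interventions 1 and 4 and the risk-factor objective.

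The size depends on shape. With a graded effect and 25% above the cut, about 54% to 65% of the information is kept, under assumed normal or doubling-dilution titre distributions. With a true step at 160, the split is the better test and should stay.

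A reader might go further and conclude that the cut for Years 2-5 should be taken from the Years 1-2 titre-risk curve. That does not follow. Those years are also the baseline for the before/after comparison in sections 3 and 8.1. A cut chosen where baseline risk happened to look high could regress and mimic a benefit. The choice of a clinical trigger is also outside a statistical review.

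This is a worthwhile, low-cost improvement. The power table needs no correction on this account.

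**What to change.** In the risk-factor objective (section 3) and in section 8.1:

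1. Keep 160 or above versus below 160 as the pre-specified contrast.
2. State that the titre is recorded as its dilution value, not only as high or low.
3. Add an analysis of log2(titre): a linear term, plus a flexible or ordered-category form to show departures from linearity.
4. Report 6-month cryptococcal meningitis-free survival with 95% confidence intervals by titre band, from Years 1-2, before titre is used in later interventions.

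The cost is that samples must be titrated to end-point instead of read only at 1:160, plus a data field for the dilution and a small amount of extra analysis. No cut-off and no management rule is proposed.
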